3.2 General study level definitions

3.2.1 Analysis time points

The following visits are recommended documentation time points and will be considered for analysis. Due to the nature of a NIS, the time points given for each visit are approximated, expected time points only.

- Visit 1, Baseline
- Visit 2 (approximately 3 months after Baseline): Visits that occurred \leq 135 days after Visit 1
- Visit 3 (approximately 6 months after Baseline or Withdrawal Visit for patients who discontinue early): All visits that occurred $>$ 135 days after Visit 1

If there are 2 visits that meet the criteria for Visit 2, then the visit nearest to the scheduled assessment time for Visit 2 will be used (i.e. 90 days after Visit 1). If there are 2 visits that meet the criteria for Visit 3, then the visit nearest to the scheduled assessment time for Visit 3 will be used (i.e. 180 days after Visit 1). No different study periods will be considered for this NIS.

However, the period for the analysis of safety variables is defined as follows:

- Observational Period: The Observational Period starts with the start date of LCM and ends at the day of study termination. In case the start date of LCM is missing, the date of Visit 1 will be used instead.

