3.3 Definition of Baseline values

Concomitant AEDs at Baseline are defined as AEDs given at the start date of LCM or the date of Visit 1 in case of a missing start date of LCM.

For all other variables, Baseline data are the values collected at Visit 1.

Baseline for the partial-onset seizure frequency per 28 days will be derived from the data of the Historical Seizure Count form as described in Section 3.10.4.

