3.5.2 Safety Set

The Safety Set (SS) is defined as all patients included in this study receiving treatment with LCM at least once in the study. The SS will be used for the analysis of the retention and discontinuation rates, time to discontinuation, safety data, and Baseline characteristics of the patients.

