3.10.3 Time since first diagnosis

The time since first diagnosis will be given in years and will be derived applying all the rules for missing date imputation (see Section 4.2.3) with the following formula:

$$(\text{Start date of LCM} - \text{date of diagnosis}) / 365.25$$

Only completed years will be considered, ie, decimal places will be ignored. In cases where the start date of LCM is missing, the date of Visit 1 will be used instead.

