3.10.7 Time to discontinuation of LCM

Time to discontinuation of LCM will be defined as

The date of last administration of LCM while in the study - the date of first dose of LCM + 1

If the date of last administration of LCM while in the study is not available the study termination date will be used. If the start date of LCM is missing, then it is assumed that the patient did not receive treatment and they would be consequently excluded from the relevant analysis sets and therefore from this analysis.

A censor flag will be derived where patients who completed the study are censored and patients who have discontinued LCM prior to the end of the 6-month Observation Period (early withdrawals) are not censored.

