4.2.3 General imputation rule for incomplete dates

Where necessary for the calculation of derived variables, partial dates will be completed using the earliest calendar date based on the partial date provided. This rule is valid for all partial dates with the exception of the following:

- Year is missing
- Start and stop dates of ADRs
- Start and stop dates of medications (see Sections 4.2.1 and 4.2.2)
- Start and stop dates of LCM
- Date of final contact
- Date of premature discontinuation

Incomplete dates for final contact and premature discontinuation, respectively, will be completed using the latest calendar date based on the partial date provided.

Start and stop dates of ADRs and LCM will not be imputed.

Completely missing dates or dates with a missing year will not be replaced, and the corresponding derived variables will be set to missing.

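### SAP 3.10.7 treats a missing lacosamide start date as proof of no treatment and excludes the patient, while SAP 3.2.1, 3.3 and 3.10.3 substitute Visit 1 and the Safety Set definition requires only that the drug was taken

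*SAP*

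**What the plan says.** Five places in the current SAP text deal with an LCM start date that is not available.

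- SAP 3.10.7 (time to discontinuation): "If the start date of LCM is missing, then it is assumed that the patient did not receive treatment". The consequence is that "they would be consequently excluded from the relevant analysis sets and therefore from this analysis". SAP 8.2.2 runs this analysis in the SS, the FAS and the modified FAS.
- SAP 3.2.1 (period for the safety variables): "In case the start date of LCM is missing, the date of Visit 1 will be used instead".
- SAP 3.3 (antiepileptic drugs at Baseline): the reference date is the LCM start date, "or the date of Visit 1 in case of a missing start date of LCM".
- SAP 3.10.3 (time since first diagnosis): "In cases where the start date of LCM is missing, the date of Visit 1 will be used instead".
- SAP 4.2.3 (incomplete dates in general): "Start and stop dates of ADRs and LCM will not be imputed".

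SAP 3.5.2 defines the SS as "all patients included in this study receiving treatment with LCM at least once in the study". Protocol 11.1 has the same definition. Neither makes membership depend on a recorded start date.

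**The concern.** One empty field gets three different instructions: exclude the patient, substitute Visit 1, or do not impute. Two programmers could follow the SAP faithfully and build different analysis sets.

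The exclusion is the instruction that does harm. It infers non-treatment from a gap in data entry and acts on set membership, not only on the variable that needs the date. The FAS is drawn from the SS and the modified FAS from the FAS, so a patient removed from the SS is removed from all three. A patient who took LCM but has no start date on file would then be missing from the adverse drug reaction (ADR) tables, the discontinuation and retention summaries, and the responder and Patient Global Impression of Change analyses.

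**Working it through.** **Step 1. Follow one patient through the rules.** Take a patient with Visit 1 documented, entries on the Drug Dosing Log or a reported ADR, a post-Baseline seizure count, and no LCM start date.

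| SAP section | Treatment of this patient |
|---|---|
| 3.5.2, 3.5.3 | In the SS (took LCM) and in the FAS (has a post-Baseline assessment) |
| 3.2.1 | Kept; safety period starts at Visit 1 |
| 3.3 | Kept; Baseline antiepileptic drugs taken at Visit 1 |
| 3.10.3 | Kept; time since diagnosis counted to Visit 1 |
| 3.10.15 | Any reported ADR counts as treatment-emergent and is analysed |
| 4.2.3 | LCM start date stays missing |
| 3.10.7 | Assumed untreated; removed from the sets |

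The last row contradicts every row above it except 4.2.3. Row 4.2.3 in turn contradicts the three Visit 1 substitutions. If 3.10.7 is applied first, the substitution in 3.2.1 can never operate in the safety tables, because SAP 10 builds those tables on the SS and modified FAS. SAP 3.10.7 is also uneven within itself: a missing last-dose date is replaced by the study termination date, but a missing first-dose date removes the patient.

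**Step 2. Is other evidence of intake collected?** Yes. SAP 3.10.14 names the Drug Dosing Log, and the Study Termination CRF for the last administration. Under Protocol 10.1.7, ADR data are extracted from the global safety database, so an ADR can be on file even when the start-date field is empty.

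**Step 3. Effect on precision.** The plan's own figure comes first (SAP 2.4: expected proportion 0.60, 93 evaluable, half-width 0.10).

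- n = 1.96² × 0.60 × 0.40 / 0.10² = 92.2, rounded up to 93. The figure reproduces.
- Half-width at 93 = 1.96 × √(0.24/93) = 0.0996.

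The documents do not say how many start dates are missing. As an assumed range, losing 1, 2, 3 or 5 of the 93 gives half-widths of 0.1001, 0.1007, 0.1012 and 0.1024. This is negligible.

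**Step 4. Effect of selective loss.** The inputs here are assumptions for illustration: an SS of 100 (the planned enrolment; the SAP gives no SS size), 10 discontinuations due to an ADR, 80 patients retained as a simple proportion, and 1 to 5 treated patients dropped.

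| Quantity | True value | Dropped patients all had the event | None of them had it |
|---|---|---|---|
| Discontinued due to ADR | 10.0% | 9/99 = 9.1% to 5/95 = 5.3% | 10/99 = 10.1% to 10/95 = 10.5% |
| Retained | 80.0% | 79/99 = 79.8% to 75/95 = 78.9% | 80/99 = 80.8% to 80/95 = 84.2% |

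In the second row the event is being retained. The larger shifts need several dropped patients who all share one outcome.

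**The case against.** The strongest defence is that the rules serve different sets. The Enrolled Set includes anyone with Visit 1 documented, treated or not. SAP 6 bases the Baseline listings on it, and SAP 10 lists ADRs on it. Under Protocol 10.1.2, reporting can begin at consent, before any dose. On this view the Visit 1 fallbacks exist for listings of patients with no start date, and 3.10.7 is a working proxy for the SS definition. The proxy fails only for a treated patient whose start date survives cleaning as a blank. That should be rare: LCM administration is documented at all three visits (Protocol Table 15-1), and computerised checks and manual review apply (Protocol 12.1.2.2).

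The rarity argument stands. The separate-sets reading is possible for parts of 3.3 and 3.10.3, but the SAP does not state it. It fits 3.2.1 poorly, because that section sets the period for safety variables that SAP 10 summarises in the SS and modified FAS. SAP 6 also runs the Baseline summaries, not only the listings, on the SS, FAS and modified FAS.

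A reader might infer more than the documents support:

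- *That a partial start date also triggers exclusion.* SAP 3.10.1 and 4.2.3 distinguish partial from missing dates, and 3.10.7 speaks only of missing ones. Leaving a partial date unimputed does not make the patient untreated.
- *That allowing LCM to start up to 7 days before enrolment makes gaps likely.* Checking Protocol selection criterion 1 requires the site to establish a recent start date. If anything, this favours a known date.
- *That a definite share of the SS would be lost.* Any count is an assumption, and 93 is the expected evaluable number, not the SS size.
- *That affected ADRs would vanish.* They would leave the summary tables but remain in the Enrolled Set listing (SAP 10).

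**Conclusion.** The exclusion in SAP 3.10.7 is wrong as written. It conflicts with the SS definition and with three other SAP rules for the same missing date, and 4.2.3 adds a further inconsistency. For any patient with evidence of LCM intake but no recorded start date, it would wrongly remove the patient from the safety summaries and both primary analyses.

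The expected size is small. The documents give no count of missing start dates, data checks should keep it very low, and the loss of precision is negligible. The point is still worth correcting before programming, because the rule decides who enters the safety and primary sets and the loss need not be random. The conclusion rests on reading the sets meant in 3.10.7 as those named in 8.2.2, which the stated reason of non-treatment supports.

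**What to change.** 1. Delete the sentence in SAP 3.10.7 that assumes non-treatment and excludes the patient.
2. In SAP 3.5.2, decide SS membership on any recorded evidence of LCM intake, such as the Drug Dosing Log or the Study Termination CRF.
3. State one rule for a missing LCM start date and apply it in 3.2.1, 3.3, 3.10.3, 3.10.7 and 4.2.3. Either of these would do:
   - Keep the patient in the sets and set only the date-dependent derivation, such as time to discontinuation, to missing. The number of such patients should be reported beside the Kaplan-Meier results. This agrees with 4.2.3 as it stands, and the Visit 1 substitutions would be removed.
   - Use Visit 1 throughout, with an explicit exception in 4.2.3. Add a note that LCM may have started up to 7 days before enrolment, so time on treatment could be understated by up to about 7 days (7/180 = 3.9% of the 180-day cut), and that it would be overstated if LCM began after Visit 1.

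The cost is SAP wording and the matching line in the programming specification. No new data are needed.

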3.10.8 EQ-5D-5L

The EQ-5D is comprised of 5 item health status measures and a visual analogue scale (VAS) scale. The EQ-5D VAS records the respondent's self-rated health state on a vertical 20 cm scale, 0 to 100 graduated (0=worst imaginable health state, 100=best imaginable health state).

Utility as converted from the 5 dimensions will be derived. Each patient's responses to the five 5-dimension questions are converted to a 'health state' which is summarized, for example, as 11111 (where the patient answered 1 to each of the 5 dimension questions). The health state is then mapped to a utility value from the most recent UK valuation set (<http://www.euroqol.org/about-eq-5d/valuation-of-eq-5d/eq-5d-5l-value-sets.html>).

Absolute scores and changes from Visit 1 (Baseline) to Visit 3 (Month 6 or end of Observational Period) for the VAS score and the utility will be derived for patients with an evaluable Baseline assessment.

3.10.9 M.D. Anderson Symptom Inventory Brain Tumor Module

The MDASI-BT includes 9 brain tumor specific symptom items in addition to the core MDASI 13 symptom items and the 6 interference items. The brain tumor specific symptom items include: weakness on one side of the body, difficulty understanding, difficulty speaking, seizures, difficulty concentrating, vision, change in appearance, change in bowel pattern (diarrhea or constipation), and irritability.

The mean core symptom severity is the mean of the 13 core symptom items. If at least 7 of the items have been scored, then the mean core symptom severity is the sum of the items answered divided by the number of items answered.

The mean module symptom severity is the mean of the 9 brain tumor specific symptom items. If at least 5 of the items have been scored, then the mean module symptom severity is the sum of the items answered divided by the number of items answered.

The mean total symptom severity is the mean of all 22 symptom items. If more than 50% of the items are answered, then the mean total symptom severity is the sum of the items answered divided by the number of items answered.

The mean interference is the mean of the 6 interference items. If more than 50% of the items are answered, then the mean interference is the sum of the items answered divided by the number of items answered.

Absolute scores and changes from Visit 1 (Baseline) to Visit 3 (Month 6 or end of Observational Period) for the individual items of the MDASI-BT, the mean core symptom severity scale, the mean module symptom severity, the mean total symptom severity and mean interference will be derived for patients with an evaluable Baseline assessment. Patients with an evaluable Baseline assessment for MDASI-BT are defined as patients who have not started LCM at the time of Visit 1.

3.10.10 Discontinuation of LCM due to an ADR

A patient who discontinued LCM due to an ADR is defined as a patient who prematurely terminated from the study and the primary reason for premature study termination = “ADVERSE DRUG REACTION”.

3.10.11 Discontinuation of LCM due to lack of efficacy

A patient who discontinued LCM due to lack of efficacy is defined as a patient who prematurely terminated from the study and the primary reason for premature study termination = “LACK OF EFFICACY”.

3.10.12 Discontinuation of LCM due to lack of effectiveness

A patient who discontinued LCM due to lack of effectiveness is defined as a patient who prematurely terminated from the study and the primary reason for premature study termination = “LACK OF EFFICACY” or “ADVERSE DRUG REACTION”.

3.10.13 Clinical Global Impression of Change

Patients will be categorized based on their CGIC value collected at Visit 3 into the following groups:

- Improved: scores 1 to 3
- No change: score 4
- Worsened: score 5 to 7

3.10.14 Exposure

Actual dosing of LCM is documented on the Drug Dosing Log CRF. The duration of exposure to LCM in days is calculated as the end date of last administration of LCM minus the start date of first administration of LCM +1. If LCM is ongoing at the end of the study, the day of last administration of study drug recorded on the Study Termination CRF will be used as the end of administration. Gaps in LCM treatment or days on the Study Medication Administration form with unknown dosing will not be subtracted from the overall exposure days.

Subject-years of exposure will be calculated as the number of days of exposure (summed over all patients), divided by 365.25.

The maximum daily dose will be calculated as the highest total daily dose the patient received during the Observational Period.

The modal dose (mg/day) will be defined as the daily LCM dose the patient received for the longest duration during the Observational Period. The modal dose calculation is based on the number of days a patient was on a given daily dose. Gaps in LCM dosing will be excluded from the determination of modal dose (ie, no imputation for days with missing dosing information will be performed). If multiple doses have the same maximum number of days of occurrence, the maximum of these doses will be used as the modal dose.

3.10.15 Adverse Drug Reactions

Adverse drug reactions will be documented during the study only. Since an ADR is an adverse event related to the medication to be investigated (LCM), all reported ADRs are considered treatment-emergent and will be included in the analysis.

An ADR with action taken regarding UCB suspected drug reported as “Permanently discontinued” will be regarded as an ADR leading to discontinuation of LCM.

Adverse drug reactions that have the question “Seriousness indicators: Is the event/reaction serious?” answered “yes” are considered as serious.

Note AESIs are collected as ADRs and will be treated as ADRs in the analysis.

Other significant ADRs will be summarized.

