4.3 Safety variables

The following safety variables will be collected:

- Occurrence of ADRs or adverse events of special interest (AESIs) spontaneously reported by the patient or observed by the treating physician
- Patient withdrawal due to ADRs

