10 ASSESSMENT OF SAFETY

For the assessment of safety of LCM, the causal relationship, seriousness, and outcome of ADRs and AESIs will be collected during the Observation Period. It is the task of the treating physician to make a judgment about a causal relationship with the LCM intake.

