10.1.7 Procedures for reporting adverse events and adverse drug reactions

The patient will be given the opportunity to report AEs spontaneously. A general prompt will also be given at each study visit to detect AEs. For example:

“Did you notice anything unusual about your health (since your last visit)?”

Following a causality assessment, the physician will document all spontaneously reported ADRs by the patient in the Adverse Event Report form. In addition, the treating physician should review any self-assessment procedures employed.

If an ADR or AESI is reported, UCB's local Drug Safety department must be informed within 1 working day of receipt of this information by the site (see contact details for safety reporting on the Study Contact Information page of this NIS observational plan). The treating physician must forward to UCB (or its representative) a duly completed Adverse Event Report form provided by UCB, even if the data are incomplete, or if it is obvious that more data will be needed in order to draw any conclusions. Information recorded on this form will be entered into the global safety database.

If clarifications on the ADR or AESI are necessary, UCB shall request additional information from the treating physician.

The Adverse Event Report form and other requested information must be provided in English.

Additional information (eg, autopsy or laboratory reports) received by the treating physician must be provided within 24 hours. All documents in the local language must be accompanied by a translation in English, or the relevant information included in the same document must be summarized in the Adverse Event Report form.

The treating physician is specifically requested to collect and report to UCB (or its representative) any ADRs or AESIs (Section 10.1.8), and to also inform participating patients of the need to inform the treating physician of any AE during the study.

At the conclusion of the study, ADR or AESI data will be extracted from the global safety database and will be analyzed along with the clinical data to allow for the final summary of the safety variables (see Section 11.3.4). The current Summary of Product Characteristics for LCM should be considered for the evaluation of ADR expectedness.

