10.1.8 Adverse events of special interest

An AESI is any AE that a regulatory authority has mandated to be reported on an expedited basis, regardless of the seriousness, expectedness, or relatedness of the AE to the administration of a UCB product/compound.

The following are the LCM AESIs:

- The following arrhythmias: atrial fibrillation/flutter, ventricular tachycardia or fibrillation, atrioventricular block (second degree, Type I and II, and third degree), and marked bradycardia (<45 beats/min)
- Syncope or loss of consciousness (other than seizure related)
- Serious suspected multiorgan hypersensitivity reactions

Serious suspected multiorgan hypersensitivity cases may be identified and reported to the sponsor by the treating physician using the following algorithm as agreed with the US Food and Drug Administration:

- An AE or laboratory value (as defined in the following text) suggestive of internal organ involvement (including but not limited to hepatitis, nephritis, pneumonitis, carditis,

colitis, encephalitis, pancreatitis, myositis, arthritis, or hematologic system involvement) combined with at least 1 of the following: fever, rash, lymphadenopathy, or eosinophilia.

- Treatment-emergent abnormal laboratory value criteria suggestive of internal organ involvement or eosinophilia:
 - Eosinophils % $\geq 10\%$
 - Eosinophils absolute $\geq 0.5\text{G/L}$
 - Neutrophils absolute $< 1.5\text{G/L}$
 - Platelets $\leq 100\text{G/L}$
 - Alanine aminotransferase $\geq 2\times$ upper level of normal (ULN)
 - Aspartate aminotransferase $\geq 2\times\text{ULN}$

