2.2.3 Safety variables

The following safety variables will be collected:

- Occurrence of ADRs or adverse events of special interest (AESIs) spontaneously reported by the patient or observed by the treating physician
- Patient withdrawal due to ADRs

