10.2 Adverse events

Adverse drug reactions will be coded for analysis with version 16.1 of MedDRA. Note that AESIs will be collected as ADRs and consequently AESIs will be included in the summary tables and listings for ADRs.

Adverse drug reactions that occur during this study will be presented by MedDRA SOC and PT in a frequency table giving the number and percentage of patients experiencing each event at least once as well as the number of events. For the number and percentage of patients, patients

with multiple ADRs will be counted only once within each PT and SOC. All table summaries will be sorted alphabetically by SOC and by decreasing relative frequency of each PT within SOC.

The following tabular summaries will be presented.

- Adverse drug reactions
- Serious ADRs
- Non-serious ADRs
- Non-serious ADRs above reporting threshold of 5% (as per the requirements for the EU agency)
- Adverse drug reactions leading to discontinuation
- Deaths
- ADRs by dose at onset (dose categories will be agreed during the DEM to obtain a sensible distribution)
- Other significant ADRs

An overall summary table of all ADRs will be presented summarizing the ADR categories given above (except non-serious ADRs above reporting threshold).

A listing of all ADRs will be provided as follows:

- Individual patients (identified by patient numbers) experiencing a given ADR grouped by SOC, High Level Term (HLT), PT, and severity.
- A glossary of all physician-reported terms, grouped by coded SOC, HLT, and PT. This table will serve as a glossary of PTs, showing which reported terms are summarized under each PT.

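### AESIs judged unrelated to lacosamide would be counted as drug reactions in the ADR tables, with no related-only count beside them (SAP 3.10.15 and 10.2; minor)

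*SAP*

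**What the plan says.** SAP 3.10.15 gives the meaning of an ADR in passing: "Since an ADR is an adverse event related to the medication to be investigated (LCM"). The same section then says: "Note AESIs are collected as ADRs and will be treated as ADRs in the analysis". SAP 10.2 repeats the rule for the outputs: "consequently AESIs will be included in the summary tables and listings for ADRs". Neither statement sets a condition on relatedness.

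Protocol 10.1.8 defines an AESI as an event with mandated expedited reporting "regardless of the seriousness, expectedness, or relatedness of the AE to the administration of a UCB product/compound". It names three groups: certain arrhythmias, syncope or loss of consciousness not due to seizure, and serious suspected multiorgan hypersensitivity.

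The physician's judgement is recorded for both kinds of event. Protocol 10 states that "the causal relationship, seriousness, and outcome of ADRs and AESIs will be collected during the Observation Period".

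Both documents treat the two as one safety variable. Protocol 4.3 has "Occurrence of ADRs or adverse events of special interest (AESIs) spontaneously reported by the patient or observed by the treating physician", and SAP 2.2.3 begins in the same way. Protocol 10.1.7 adds that, when the study ends, "ADR or AESI data will be extracted from the global safety database" for the final safety summary.

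**The concern.** A reader who takes the SAP's definition at its word will read a rate in an ADR table as a rate of events attributed to LCM. The AESI rule breaks that reading for a small class of events: those collected because a regulator wants them, which the treating physician judged not to be caused by LCM.

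Tolerability is the study's secondary objective, and the ADR tables are a main way of reporting it. One of them, non-serious ADRs above 5%, is produced for a regulatory requirement. If unrelated AESIs sit in these tables unmarked, the counts can overstate drug reactions and the reader cannot undo this from the tables. The judgement needed to separate the events is, according to Protocol 10, already being collected.

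**Working it through.** The plan states no figure on this point, so the check is of the text, followed by arithmetic for scale.

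**1. Can an unrelated event reach the ADR tables?**
- *Ordinary ADRs: no, if the plan is followed.* Under Protocol 10.1.7 the physician assesses causality before documenting events the patient reports as ADRs. An event judged unrelated, and not an AESI, is not recorded as an ADR.
- *AESIs: yes.* Protocol 10.1.8 makes them reportable without regard to relatedness, and SAP 3.10.15 and 10.2 place all of them with the ADRs.

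The route is therefore open for AESIs only.

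**2. Does any planned output separate them?**
- SAP 10.2 plans tables of all ADRs, serious, non-serious, non-serious above 5%, leading to discontinuation, deaths, by dose at onset and other significant ADRs, plus an overall summary. None is restricted to related events or split by relatedness.
- SAP Table 13-1 (other significant ADRs) lists preferred terms for the arrhythmia group and for syncope and loss of consciousness. It has no entry for the multiorgan hypersensitivity group and makes no use of causality.
- SAP 3.1 promises a complete set of listings. SAP 10.2 names severity and the MedDRA levels as grouping variables for the ADR listing and does not mention causality. It does not say which columns the listing has.
- SAP 4.2 sets defaults for missing action taken and missing seriousness, but none for missing causality.

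**3. What is the effect on the any-ADR rate?**

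Inputs: N = 100 (planned enrolment, assuming all receive LCM and enter the Safety Set); N = 93 (planned evaluable number, used here as an assumed modified FAS size); k = patients whose only event is an unrelated AESI (not given in the documents, so assumed).

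Added percentage points = 100 × k / N.

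- k = 0: 0 at either N.
- k = 1: 100 × 1/100 = 1.0; 100 × 1/93 = 1.1.
- k = 3: 100 × 3/100 = 3.0; 100 × 3/93 = 3.2.

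For example, if 20 of 100 patients had a related ADR and 3 others had only an unrelated AESI, the table would show 23/100 = 23.0% where the related-only rate is 20/100 = 20.0%. A patient who has both a related ADR and an unrelated AESI leaves the any-ADR rate unchanged, but adds to the event count and may add to a preferred-term row.

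**4. What is the effect on the table with the 5% threshold?**

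Only unrelated, non-serious AESIs in the same preferred term count. One such patient matters only at the margin: 5/100 = 5.0% (not above 5%) becomes 6/100 = 6.0%; 4/93 = 4.3% becomes 5/93 = 5.4%. These counts were chosen to sit at the cut-off and are not a forecast.

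**The case against.** The strongest reply is that this is a disclosed convention. The SAP states twice that AESIs are handled as ADRs, and pooling follows the combined safety variable in both documents. With about 100 patients, a reader could sort the few affected events from the listings. Table 13-1 already isolates two of the three AESI groups by preferred term, and the third would appear in the serious ADR table. Any error can only overcount drug reactions; it cannot hide an event.

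Most of this stands, and it is why the point is minor. Two things remain. Disclosing the rule does not make the label accurate while the same section defines an ADR as related. And a listing, even one that shows causality, does not supply a related-only rate.

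A reader might infer more than the documents support:
- *That the ADR tables as a whole lack a causality filter.* They do not. Ordinary ADRs are screened when recorded (Protocol 10.1.7).
- *That pooling is an undeclared departure from the protocol, because Protocol 11.3.4 speaks only of ADR tables and SAP 3.9 declares no changes.* Protocol 4.3 names the combined variable, and Protocol 10.1.7 sends both kinds of event to the safety summary with a reference to 11.3.4.
- *That the secondary variable on stopping LCM because of an ADR is contaminated.* SAP 3.10.10 derives it from the main reason given for ending the study early, not from the event records.
- *That the SAP 4.2 defaults make this a larger problem.* An unrelated AESI with action taken missing would indeed be tabulated as leading to discontinuation, and one with seriousness missing as serious. Nothing in the documents suggests that either combination is likely.

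**Conclusion.** The point holds in a narrow form. The SAP defines ADRs as related to LCM, counts every AESI as an ADR, and plans no table that uses the recorded causality. An AESI judged unrelated would be reported as a drug reaction.

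The size is about 1 percentage point on the any-ADR rate for each patient whose only event is such an AESI, at an assumed N of 100. The number of these patients is not given and may be zero. The study has one arm and no inferential analyses (SAP 4), so the consequence is a possible descriptive overstatement. No primary or secondary variable has been shown to be affected. Severity: minor.

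The conclusion assumes that the physician's causality judgement for AESIs is held as Protocol 10 says, so that label and record can disagree. The annotated case report form and the structure of the safety extract are not available to confirm this.

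A reader might also connect this with whether events before the first dose enter the tables, or with the differing rules on partial ADR dates in SAP 4.2.1 and 4.2.3. Those are separate questions of timing and are not part of this point.

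**What to change.** In SAP 3.10.15 and 10.2:

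1. Keep the pooled tables, since they match the combined safety variable, and retitle them 'ADRs and AESIs'. Reserve the term ADR for events assessed as related.
2. Show related-only counts and percentages alongside the pooled ones, using the causality collected under Protocol 10. Count missing causality as related, in line with the cautious defaults SAP 4.2 already uses for action taken and seriousness.
3. Add one AESI summary, split into related and not related, covering all three groups in Protocol 10.1.8, including multiorgan hypersensitivity, which Table 13-1 leaves out.
4. Name causality as a column in the listing of ADRs and AESIs.

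The cost is a few sentences of SAP text, new table titles, an extra column set, one missing-causality rule and one added table. Programming is minor if causality is in the extract from the global safety database; this should be confirmed before the wording is settled. No new data collection should be needed, because Protocol 10 already calls for the judgement.
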